12.5.2.2.5. Quality of Life Assessments

Quality of life, as measured by EORTC QLQ-C30, will be evaluated for subjects with a baseline assessment and at least 1 post-baseline QLQ-C30 assessment that generate a score. For total QLQ-C30, each domain score (eg, physical functioning, role functioning, emotional functioning, cognitive functioning, social functioning), as well as symptom scales, baseline values, and change from baseline for each time point will be summarized by treatment arm using descriptive statistics. Mixed models will also be applied and the details will be specified in the SAP.

Health economic measures, as assessed by the EQ-5D-5L, will be evaluated for subjects with a baseline assessment and at least 1 post-baseline EQ-5D-5L assessment that generate a score. Scores at baseline and change from baseline scores for each time point will be quantified with descriptive statistics by treatment arm.

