7.7.3.4.1. Descriptions of Questionnaires

7.7.3.4.1.1. European Organization of Research and Treatment of Cancer – Quality of Life Questionnaire – Core Questionnaire (EORTC-QLQ-C30)

The EORTC QLQ-C30 is a validated and reliable self-reported measure of QoL for subjects with cancer who are receiving cancer treatment. The QLQ-C30 contains 30 items in total and each item is a 4-point or 7-point Likert scale. These 30 items can be categorized into 1 global health status/HRQOL scale, 5 functional scales, 3 symptom scales, and 6 single item scales. Each of the multi-item scales includes a different set of items. No item occurs in more than one scale:

- 1 global health status scale (2 items)

- 5 functional scales: physical function (5 items), role function (2 items), emotional function (4 items), cognitive function (2 items), social function (2 items)
- 3 symptom scales: fatigue (3 items), nausea and vomiting (2 items), pain (2 items)
- 6 single-item scales relating to dyspnea, insomnia, appetite loss, constipation, diarrhea, and financial difficulties

7.7.3.4.1.2. EuroQoL EQ-5D-5L (EQ-5D-5L)

The EuroQoL EQ-5D-5L is a widely used standardized measure of health status that provides a descriptive profile and single index value to appraise respondents' health status. The measure was designed for both clinical and economic appraisal and has been validated in numerous clinical populations. The EQ-5D-5L is comprised of five single-item dimensions: mobility, self-care, usual activities, pain/discomfort and anxiety/depression. These dimensions are measured on a 5-level scale: “No problems”, “Slight problems”, “Moderate problems”, “Severe problems”, and “Extreme problems.”

EQ-5D-5L responses can also be converted into summary index values, using established population-based value sets. Index values reflect general population valuations of a given health state, as constituted by the EQ-5D-5L responses, where a score of 0 is equivalent to being dead and 1 is equivalent to perfect health.

The EQ-5D-5L also contains a visual analog scale (VAS) to assess the subject's overall health on a scale of 0 (“The worse health you can imagine”) to 100 (“The best health you can imagine”).

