7.7.3.4.2. Statistical Analyses

Scores for the EORTC QLQ-C30 and EQ-5D-5L will be summarized at each visit where data are available.

Completion rates will be calculated for each instrument at each assessment visit as the proportion of subjects alive at the assessment visit with a completed instrument.

7.7.3.4.2.1. EORTC-QLQ-C30

Each scale will be transformed into a 0-100 score following EORTC guidelines:

- Estimate the average of the items that contribute to the scale; this is the raw scale score
- Use a linear transformation to standardize the raw scale score, so that it ranges from 0 to 100. $\text{Scale score} = (\text{raw score} - 1) / \text{range} * 100$, where range is the difference between the maximum and minimum possible value of the raw score from each item

Transformed scores for each scale, and the absolute and percent changes from baseline will be summarized by treatment arm at each visit.

Mixed models will also be applied in the analysis of the EORTC QLQ-C30. All available data for each subject will be used in the analysis. The mixed model on the change from

baseline across visits for all scales will be performed with baseline score, treatment arm, time, randomization stratification factors and an interaction between treatment arm and time as fixed effect, and subject as random effects. All parameter estimates will be obtained using restricted maximum likelihood. The unstructured covariance structure will be used to define covariance between random effects (using option “Type=UN” as a part of the RANDOM statement in PROC MIXED). For the degrees-of-freedom calculations the Kenward and Roger algorithm will be used (using option “ddfm=kr” as a part of the MODEL statement in PROC MIXED). The least square means and 95% CI will be summarized and graphically presented by treatment arm over time.

7.7.3.4.2.2. EQ-5D-5L

The first response is coded as a 1 (indicating no problems), the second response is coded as a 2 (indicating slight problems), the third response is coded as a 3 (indicating moderate problems), the fourth response is coded as a 4 (indicating severe problems), the fifth response is coded as a 5 (indicating extreme problems). Ambiguous responses (eg, more than 1 response in a dimension) are treated as missing values.

For each dimension, the number and percentage of subjects with no problems, slight problems, moderate problems, severe problems and extreme problems will be summarized by treatment arm at each visit.

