EQ-5D-5L responses will also be converted into index values using a US value set. Summary statistics for index scores and the absolute and percent change from baseline will be reported by treatment arm at each visit.

The EQ-5D-5L also contains a utility scale of health state (VAS) ranging between 0 (worst health) and 100 (best health). Summary statistics for VAS scores and the absolute and percent change from baseline will be reported by treatment arm at each visit.

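### Percent change from baseline on the QLQ-C30 scales, EQ-5D index and VAS is undefined at a baseline of 0 and asymmetric elsewhere, so the by-arm percent tables can show a change where there is none (minor)

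*SAP*

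**What the plan says.** SAP 7.7.3.4.2.1 rescales each QLQ-C30 scale: "Use a linear transformation to standardize the raw scale score, so that it ranges from 0 to 100". The printed formula is (raw score - 1)/range × 100. For the transformed scores it then plans that "the absolute and percent changes from baseline will be summarized by treatment arm at each visit".

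SAP 7.7.3.4.2.2 does likewise for the EQ-5D index ("Summary statistics for index scores and the absolute and percent change from baseline will be reported by treatment arm at each visit") and for the VAS ("Summary statistics for VAS scores and the absolute and percent change from baseline will be reported by treatment arm at each visit").

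SAP 7.7.3.4.1 describes the instruments. For the QLQ-C30, "each item is a 4-point or 7-point Likert scale", and there are "6 single-item scales relating to dyspnea, insomnia, appetite loss, constipation, diarrhea, and financial difficulties". The EQ-5D index is anchored "where a score of 0 is equivalent to being dead and 1 is equivalent to perfect health".

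Protocol 12.5.2.2.5 lists, for the QLQ-C30, "baseline values, and change from baseline for each time point", and for the EQ-5D-5L scores at baseline and change from baseline. It does not mention percent change. Neither document says what to do when the baseline is 0, and Protocol 12.11 rules out imputation unless otherwise specified.

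**The concern.** Percent change divides by the baseline score, and that causes two problems on these scales.

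First, a baseline of 0 gives no result. On a QLQ-C30 symptom scale 0 is the symptom-free end, so the subjects lost are those with no room to improve. The exclusion is therefore related to outcome. Emergent symptoms are plausible in this trial: Protocol 5.2.3.2 reports nausea in 60.9%, diarrhoea in 56.5% and constipation in 52.2% of the 23 subjects given the combination in the Phase 1b study, and the QLQ-C30 has a scale for each. A subject who starts without the symptom and develops it cannot appear in the percent table.

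Second, above 0 a rise and a fall of equal size do not cancel. The mean percent change can move away from zero when the mean score has not moved.

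Quality of life is a stated secondary objective (Protocol 6.1.2). The by-arm percent tables would stand beside absolute-change tables for the same scale and could contradict them.

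**Working it through.** **Score grid.** Using the SAP formula, an item coded 1 to 4 has range 3. Codes 1, 2, 3 and 4 give 0, 33.3, 66.7 and 100, which reproduces the stated range of 0 to 100. A 7-point item gives 0 to 100 in steps of 16.7. The SAP does not print the item coding. I take the lowest code on a symptom item to mean no symptom, and the single items to be 4-point.

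**Undefined at 0.** Percent change = 100 × (follow-up - baseline)/baseline. At baseline 0 the divisor is 0. The share of subjects lost from a scale's percent table equals the share at 0 at baseline.

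**Asymmetry above 0.** On the 4-point grid the largest fall is -100% and the largest rise is +200% (33.3 to 100). In each pair below, two subjects exchange scores, so the mean absolute change is exactly 0:

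| Swap | Percent changes | Mean |
|---|---|---|
| 33.3 and 66.7 | +100, -50 | +25% |
| 33.3 and 100 | +200, -66.7 | +66.7% |
| 66.7 and 100 | +50, -33.3 | +8.3% |
| 0 and 33.3 | undefined, -100 | -100% |
| EQ-5D index 0.4 and 0.8 | +100, -50 | +25% |
| EQ-5D index 0.7 and 0.9 | +28.6, -22.2 | +3.2% |

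The fourth row goes the other way: the subject who worsened is lost and only the one who improved is counted.

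**A whole arm with no net change.** Let the score X have the same distribution at both visits. If the visits are independent, the mean percent change among computable subjects is 100 × (E[X] × E[1/X given X > 0] - 1). If half the subjects are unchanged and the rest are independent, the result is halved. The documents give no baseline distribution, so those below are assumptions.

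Worked case with 40% at 0 and 30%, 20% and 10% at the other levels: E[X] = 33.3; E[1/X given X > 0] = (0.3/33.3 + 0.2/66.7 + 0.1/100)/0.6 = 0.02167; the product is 0.722, so the mean is -27.8%.

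| Share at 0 / 33.3 / 66.7 / 100 (%) | Independent visits | Half unchanged |
|---|---|---|
| 0 / 50 / 30 / 20 | +21.8% | +10.9% |
| 10 / 45 / 30 / 15 | +8.3% | +4.2% |
| 20 / 40 / 25 / 15 | -3.0% | -1.5% |
| 25 / 25 / 25 / 25 | -8.3% | -4.2% |
| 40 / 30 / 20 / 10 | -27.8% | -13.9% |
| 60 / 25 / 10 / 5 | -52.5% | -26.3% |
| 80 / 12 / 5 / 3 | -76.0% | -38.0% |

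For a two-item symptom scale (seven levels, half unchanged), with non-zero subjects split 30/25/20/12/8/5% over the levels from 16.7 to 100, the means are +13.4%, -0.7% and -14.8% at 10%, 30% and 50% at 0. Under these distributions the sign turns at roughly 15% to 30% at 0.

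**Absolute change on the same data.** The mean is 0.0 in every row, and every subject with a baseline is kept, including those at 0.

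**The case against.** The case for leaving the SAP alone is substantial, and most of it stands.

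- The percent summaries are additional. The same sentences provide observed scores and absolute change. The QLQ-C30 mixed model uses change from baseline, adjusts for the baseline score and uses all available data, so it keeps subjects at 0. New symptoms reported as adverse events are summarized separately (SAP 7.8.1).
- No inference depends on the percent tables. Quality of life is outside the fixed testing sequence, and Protocol 12.5 claims no alpha control for it.
- The loss would be visible. SAP 6.4.4 requires the count of non-missing values, so a smaller n for percent change would show at each visit. It also requires medians and quartiles, which may soften the skew but do not restore the excluded subjects.
- A reader might infer a breach of the protocol. The documents do not support that. SAP section 2 allows the SAP to modify the protocol's plans, and only major changes to the primary endpoint or its analysis must also go into an amendment.
- A reader might infer that no net change will generally look like worsening. That also fails. It happens on higher-is-worse scales with few baselines at 0. With more subjects at 0 the table shows apparent improvement.
- A reader might extend the loss of symptom-free subjects to the EQ-5D index. A subject in perfect health has an index of 1, not 0, and does not drop out. On the index and VAS higher is better, so an upward artefact reads as improvement.

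What remains is that the statistic is undefined for an outcome-related group on the symptom scales, distorted elsewhere, and has no zero-baseline rule.

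**Conclusion.** The point holds as a minor one. By-arm percent change on these scales can show worsening or improvement when nothing has changed. The direction depends on scale polarity and on the share of subjects at 0. In the single-item scenarios with no net change, the artefact runs from +21.8% to -76.0%; the true mean change is 0 throughout.

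That range rests on assumed baseline distributions with 0% to 80% at 0, on 4-point single items, and on follow-up scores that are independent or half unchanged. It shows what can happen and is not a forecast for this trial. The division by zero and the swap examples need no assumed distribution.

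The documents do not support the stronger conclusion that the quality-of-life analysis as a whole is compromised or that emergent symptoms go unreported. The effect is confined to the descriptive percent tables.

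**What to change.** In SAP 7.7.3.4.2.1 and 7.7.3.4.2.2, delete percent change from baseline for the QLQ-C30 scales, the EQ-5D index and the VAS. Report observed scores and absolute change only, which matches Protocol 12.5.2.2.5.

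If the percent columns are kept, the minimum is a stated rule for a zero baseline, the number excluded per arm and visit, and the direction of each scale in the table.

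Deletion costs a few words and produces fewer tables. It needs no new data, does not touch the mixed model, and leaves power and alpha unchanged.

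### As written, the QLQ-C30 mixed model reduces to compound symmetry, so its by-visit 95% intervals will be too wide early and too narrow late if variance or correlation changes over time

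*SAP*

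**What the plan says.** Protocol 12.5.2.2.5 leaves the model to the SAP: "Mixed models will also be applied and the details will be specified in the SAP".

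SAP 7.7.3.4.2.1 then gives these elements:

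- **Response and fixed effects.** The response is the change from "baseline across visits for all scales will be performed with baseline score, treatment arm, time, randomization stratification factors", plus an interaction between "treatment arm and time as fixed effect, and subject as random effects".
- **Random effects.** Subject is the only one named. No random slope or random visit effect is listed.
- **Covariance.** "The unstructured covariance structure will be used to define covariance between random effects", with the option placed "as a part of the RANDOM statement in PROC MIXED". No REPEATED statement or residual structure is mentioned.
- **Estimation.** "All parameter estimates will be obtained using restricted maximum likelihood". "For the degrees-of-freedom calculations the Kenward and Roger algorithm will be used".
- **Output.** LS means with 95% CIs, tabulated and plotted by arm over time. No between-arm contrast or p-value is listed.

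The SAP does not say whether time is categorical. The protocol's Schedule of Assessments (Table 6, footnote 21) puts QoL at Weeks 1, 3, 5 and 7, then at Weeks 9, 17, 25 and so on, at EOT, and 4 weeks post-treatment. Neither document gives an SD, a correlation or a dropout rate for QLQ-C30 scores.

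**The concern.** A reader who sees the word unstructured will expect a model in which each visit has its own variance and each pair of visits its own correlation. The elements listed do not produce that model. They produce the most restrictive of the common repeated-measures structures, and apply it to a change-from-baseline response that runs from Week 3 to a year or more.

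That structure gives every visit the same residual variance. If the true residual variance rises with time since baseline, early intervals are too wide and late ones too narrow. The model covers all QLQ-C30 scales, and its LS means and intervals are the only model-based QoL output in the SAP (EQ-5D-5L is summarized descriptively). At stake is how precise the late part of each plotted curve appears.

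**Working it through.** The plan states no figure for this model, so there is none to reproduce.

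**Step 1: structure.** The marginal covariance is V = ZGZ′ + R. With a subject intercept only, Z is a column of ones and G is the single number σ_b². With no REPEATED statement, R = σ_e²·I. So V = σ_b²·J + σ_e²·I, where J is the matrix of ones. For example, σ_b² = 7 and σ_e² = 5 give 12 in every diagonal cell and 7 in every other cell. That is compound symmetry. TYPE=UN on a 1×1 G changes nothing.

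**Step 2: what this does to a by-visit interval.** Inputs from the documents are the QoL weeks (3, 5, 7, 9, 17, 25, 33, 41, 49), baseline at Week 1, and one baseline coefficient common to all visits. The assumptions, which the documents do not give, are complete data, raw-score variance 1 at every visit, reliability r, and true-score correlation decaying by a factor ρ per 4 weeks.

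- Correlation with baseline: c_t = r·ρ^((t−1)/4)
- Common baseline slope: b = mean of c_t over the nine visits
- Residual variance: v_t = 1 − 2b·c_t + b²
- With balanced data, σ_b² + σ_e² estimates the mean of v_t, written v̄. Model SE over true SD is therefore √(v̄/v_t).
- Coverage: 2Φ(1.96·√(v̄/v_t)) − 1, leaving aside the small contribution from estimating b

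For ρ = 0.90 and r = 0.8:

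- c_3 = 0.8 × 0.9^0.5 = 0.759; c_49 = 0.8 × 0.9^12 = 0.226; b = 0.512.
- The nine v_t are 0.485, 0.525, 0.563, 0.599, 0.725, 0.827, 0.910, 0.977 and 1.031, with mean 0.738.
- Week 3: √(0.738/0.485) = 1.23, coverage 98.4%.
- Week 49: √(0.738/1.031) = 0.85, coverage 90.3%.

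| ρ per 4 weeks | r | v_3 | v_49 | v̄ | SE/SD, Week 3 | SE/SD, Week 49 | Coverage, Week 3 | Coverage, Week 49 |
|---|---|---|---|---|---|---|---|---|
| 0.85 | 0.7 | 0.658 | 1.065 | 0.861 | 1.14 | 0.90 | 97.5% | 92.2% |
| 0.85 | 0.9 | 0.435 | 1.107 | 0.771 | 1.33 | 0.83 | 99.1% | 89.8% |
| 0.90 | 0.8 | 0.485 | 1.031 | 0.738 | 1.23 | 0.85 | 98.4% | 90.3% |
| 0.95 | 0.7 | 0.551 | 0.887 | 0.695 | 1.12 | 0.88 | 97.2% | 91.7% |
| 0.95 | 0.9 | 0.258 | 0.814 | 0.495 | 1.38 | 0.78 | 99.3% | 87.4% |
| 1.00 (no decay) | any | equal | equal | equal | 1.00 | 1.00 | 95.0% | 95.0% |

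A 2,000-replicate simulation of the middle case (100 per arm, no treatment effect) left zero outside the interval for the arm difference in 1.8% of runs at Week 3 and 10.4% at Week 49. That is coverage of 98.2% and 89.6%, in line with the formula.

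**Step 3: other covariances, and dropout.** These simulations used 1,000 trials per scenario, 100 per arm and the same visits. Residual correlation was either 0.6 at all lags or 0.9 per 4 weeks. Residual SD was either 20 throughout or rising from 15 to 25. Dropout, where present, depended on the last score and left 48% complete at Week 49. All of these are assumptions. The Monte Carlo standard error near 95% is √(0.95 × 0.05/1000) = 0.7 points.

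| Residual truth | Dropout | Control LS-mean coverage, Week 3 → Week 49, model as written | Same, unstructured across visits |
|---|---|---|---|
| Exchangeable, constant SD | no | 93.7% → 94.6% | not run |
| Exchangeable, constant SD | yes | 94.9% → 94.5% | not run |
| Decaying, constant SD | no | 94.3% → 95.8% | not run |
| Decaying, constant SD | yes | 95.6% → 80.9% | 95.0% → 94.2% |
| Decaying, rising SD | no | 99.2% → 87.5% | not run |
| Decaying, rising SD | yes | 98.5% → 81.1% | 94.5% → 92.2% |

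For the arm difference, the unstructured fit covered 94–96% at every visit in both scenarios where it was run.

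**Step 4: Kenward-Roger.** This method adjusts for estimating the parameters of the assumed structure. It does not give visits separate variances, so it leaves the ratios in Step 2 essentially unchanged.

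**The case against.** The strongest reply is that the text is incomplete rather than wrong. It speaks of covariance between random effects, in the plural, which suggests that several were intended. Random visit effects within subject with TYPE=UN would be unstructured across visits, and an intercept plus slope would also make the option meaningful. This stands as a reading of intent, but the SAP lists neither. A programmer who follows the list gets compound symmetry.

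It also means a reader should not infer that the SAP promises an unstructured matrix across visits and then contradicts itself in code. Its wording and its option agree with each other; both apply to the random effects.

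A second reply is that the intervals may be perfectly good. This stands as well. They are calibrated under a compound-symmetric truth, with or without the dropout simulated. They are also calibrated when residual variance is constant and data are complete, even if residual correlation decays. The answer to that last case is only partial. If raw scores have constant variance and their correlation with baseline decays, the residual variance after baseline adjustment must rise (Step 2), so constant residual variance is not what such scores produce. That remains an argument from plausibility, because the documents give no covariance.

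A reader might also infer an inflated type I error for a QoL treatment comparison. The documents do not support that: the SAP plans LS means and intervals by arm and names no contrast or p-value for this model. Nor do they plan a QoL claim for late visits or for responders.

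**Conclusion.** The structural point holds without condition on the text as written: TYPE=UN has no effect and the model is compound symmetry.

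Miscalibration is conditional. With decay of 0.85–0.95 per 4 weeks, reliability 0.7–0.9 and complete data, by-visit coverage is about 97–99% at Week 3 and 87–92% at Week 49. Score-dependent dropout can take late LS-mean coverage to about 81% in the decaying-correlation scenarios above. With no decay and constant variance it is 95% throughout. A flat statement that the intervals are miscalibrated would go beyond the documents.

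The consequence is limited. QoL is an additional secondary endpoint, and Protocol 12.5 leaves it outside the alpha-controlled sequence. EFS and the key secondary tests are untouched. The change is still worth making, because following the SAP literally gives a less reliable result than an inexpensive alternative.

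**What to change.** In SAP 7.7.3.4.2.1:

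1. State that time is categorical, defined by scheduled visit. Say how EOT and 4-week post-treatment scores enter, since they fall at no fixed study week.
2. Replace the RANDOM subject specification carrying TYPE=UN with REPEATED visit / SUBJECT=subject TYPE=UN, keeping REML and DDFM=KR. If other random effects were intended instead, list them.
3. Prespecify a heterogeneous-variance fallback if the fit does not converge, for example TOEPH, then ARH(1).

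The cost is a few lines of SAP text and a changed model statement; no new data are needed. The real downside is the number of covariance parameters: for nine visits, 9 × 10/2 = 45 against 2 as written, with possible non-convergence where late visits are sparse. TOEPH needs 9 + 8 = 17 and ARH(1) 9 + 1 = 10. Both fallbacks tie correlation to visit order rather than elapsed time, and the visits are unevenly spaced, so they are second best, but they do let variance differ by visit.
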